been speculated that neuronal hyperexcitability as a direct consequence of persistent inward sodium current results in reverse operation of the $\text{Na}^+ \text{-Ca}^{++}$ exchanger, intracellular and intraxonal Ca^{++} , and motor neuron degeneration by activation of Ca^{++} -dependent enzyme pathways [32]. Increased repetitive firing of cortical motor neurons following injection of current using current clamp conditions in $\text{SOD1}^{\text{G93A}}$ mice relative to age-matched controls has also been shown [27, 28], correlating with cortical hyperexcitability in the mutant mice. A recent study by Wainger and colleagues also demonstrated that inducible pluripotent stem cell-derived (IPS) motor neurons from ALS patients with superoxide dismutase 1, C9orf72, and fused-in-sarcoma mutations had evidence of hyperexcitability as a consequence of reduced delayed-rectifier potassium current compared to control IPS motor neuron cells from control cells [33]. Additionally, the Kv7 channel activator retigabine was able to block the hyperexcitability and improve survival of the cells *in vitro*, suggesting that it could also be a putative disease modifying therapy [33]. Studies employing TMS have demonstrated that RMT and SICI are reduced and MEP increased in both clinically affected familial ALS and SALS patients when compared to asymptomatic SOD1 mutation carriers and normal controls, consistent with increased cortical hyperexcitability in the patients [31]. Threshold tracking nerve conduction studies have also demonstrated hyperexcitability of peripheral motor nerve axons as a consequence of increased persistent sodium current [29, 30], which could also play a role in the generation of fasciculations and muscle cramps, problematic and poorly treated symptoms in ALS. Additionally, by this technique, there is evidence that measurement of the strength-duration time constant, reflecting axonal persistent sodium currents, inversely correlates with survival in ALS [29].

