4.0. STUDY DESIGN

4.1. Overall Study Design and Plan

During the enrollment period, approximately 90 sporadic ALS (sALS) patients will be screened at approximately 9 Northeast ALS Consortium (NEALS) centers in the US. Approximately 60 eligible sALS subjects will be randomly assigned in a 1:1:1 ratio to oral mexiletine 300 mg/day, 600 mg/day or matching placebo. After randomization, subjects will undergo the Baseline Visit and take their first dose of study drug in clinic at that visit. All visit windows are consecutive calendar days and are calculated from the day the participant has their Baseline Visit (Day 1).

In the phase II study, within three weeks following screening, RMT will be assessed by single pulse TMS prior to initiating study drug (baseline), four weeks after initiating placebo or mexiletine at either 300 mg or 600 mg per day, and then again after a four week washout period. Therefore, there will be a total of four visits (screening, baseline, week 4, and week 8). To ensure tolerance, the medication dose will be escalated over the course of one week. The RMT will serve as a pharmacodynamic marker of the effects on cortical excitability in ALS using this medication. The goal of these studies is to determine if targeting this putative mechanism of motor neuron injury in ALS reduces this excitability (significantly increases the RMT), which may serve as a pathogenic mechanism for the disease, potentially slowing progression in ALS.

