3.3 Measurement Definitions

3.3.1 TMS Measures

Transcranial magnetic stimulation (TMS) is a neurophysiologic test for assessing upper motor neuron function. A magnetic coil is positioned on the head above the motor cortex at a location that causes excitation of the abductor pollicis brevis (APB) muscle in a participant's dominant hand. High-frequency sampling of motor evoked potentials (MEP) in the APB is used to record neurophysiologic response to specific magnetic field strengths and sequences. The MEP traces are used to calculate a range of derived measures. MEPs that were below the limit of detect and recorded as zero mV were replaced by 0.005 mV.

- Resting motor threshold (RMT): RMT is the magnetic field strength, measured as a percentage of the maximum stimulator output, that produces at least a 0.05 mV response in at least 5 of 10 consecutive trials.

- Maximum MEP amplitude: Maximum MEP amplitude is defined as the maximum MEP elicited as a percentage of the maximum CMAP.
- Input/Output curve parameters: MEPs elicited by stimuli ranging in strength from 60% of RMT to 150% of RMT follow a sigmoidal curve with upper and lower thresholds and a smooth, symmetric transition between the thresholds. A four-parameter logistic function fit to the input/output curve after log-transformation of output potentials yields estimates of maximum amplitude, minimum amplitude, midpoint of activation, and slope at the midpoint of activation.
- Cortical silent period (CSP): CSP is the suppression of voluntary muscle contraction elicited by stimulation equal to 120% of RMT. CSP duration is measured from the time of the muscle activity suppression to return of muscle activity.
- Short-interval intracortical inhibition (SICI): Paired-pulse SICI is defined as the ratio of the response after a conditioning pulse equal to 80% of RMT is administered 3 ms prior to the signaling pulse divided by MEP amplitude. SICI is calculated as the geometric mean of replicate estimates.
- Intracortical facilitation (ICF): Paired-pulse ICF is defined as the ratio of the response after a conditioning pulse equal to 80% of RMT is administered 15 ms prior to the signaling pulse divided by MEP amplitude. ICF is calculated as the geometric mean of replicate estimates.

TMS tracings are centrally reviewed and processed. The central reader indicates the reliability of the overall TMS assessment and of individual measures using a set of quality flags:

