3.4 Determination of Sample Size

[name] (personal communication) reports a mean 4-week change in RMT among 18 ALS patients of 6.2% and a SD of 5.1%. A sample size of 60 participants randomized 1:1:1 with up to 10% loss to follow-up would provide 80% power to detect an effect of a given dose of mexiletine on RMT if the increase in RMT relative to placebo is at least 5.3% based on a simple one-way ANOVA and two-sided alpha = 0.027 for each of the two active arms. This estimate of power is conservative relative to our proposed shared-baseline mixed model analysis. This effect is roughly 85% of the natural variation in RMT over 4 weeks. Power will also be greater if a linear dose-response is present, with 80% power to detect a slope of 2.4% / 300 mg dose. Selection of the active dose exhibiting greater increase in RMT in our sample, irrespective of compliance with assigned dose and thus reflecting variation in tolerance, will correctly identify the dose with greater true ITT efficacy with at least 80% probability if the difference in efficacy is at least 1.4%.

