3.7 Pharmacodynamic and Clinical Analyses

3.7.1 Primary Analysis of the Primary Pharmacodynamic Endpoint

The primary pharmacodynamic analysis will test the effect of mexiletine on RMT in the mITT sample using a shared-baseline mixed model with fixed effects for visit (4 levels: Screening, Baseline, Week 4, and Week 6), treatment group (3 levels: placebo and 300 and 600 mg/day mexiletine) x post-baseline visit (2 levels) and random participant-specific intercepts and slopes with unstructured covariance. The interaction between fixed effects for treatment group and visit will be restricted to post-baseline visits by including a numeric indicator variable (0 pre-treatment, 1 post-treatment) in the interaction. Use of a shared baseline reflects the true state of the population sampled prior to randomization and has the advantage of adjusting for any chance differences at baseline in a manner similar to analysis of covariance (Liang and Zeger, 2000) with potentially greater efficiency with more than one follow-up visit and drop-out. Random participant-specific slopes will be estimated per month from treatment initiation. Data from Final Safety Visits will be assigned to the closed scheduled post-baseline visit. The following SAS code specifies the model:

```
proc mixed data=xxx method=reml;
  class id trtrnd visit;
  model Value = visit post*trtrnd*visit;
  random intercept month / subject=id type=un;
```

The primary estimand will be the comparison of the average change in RMT from pre-treatment to Week 4 for the two active groups vs. placebo, tested using a two-tailed Wald-test at alpha = 0.05. The estimate and its 95% confidence bounds will be obtained by a linear contrast of adjusted means. The following SAS code specifies the linear contrast (with the sort order for treatment group being placebo, 300 mg/day mexiletine, and 600 mg/day mexiletine, and the sort order for visit being chronological):

```
estimate "3|ActvsPlb|dWk 04"
  post*trtrnd*visit 0 0 -2 0  0 0 1 0  0 0 1 0 / cl divisor=2;
```

A significant mean reduction in RMT from pre-treatment to the Week 4 among participants randomized to either 300 or 600 mg/day mexiletine relative to mean changes among participants randomized to placebo would be considered evidence that mexiletine is effective in reducing cortical hyperexcitability.

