3.7.2 Secondary Analyses of the Primary Pharmacodynamic Endpoint

Several secondary analyses will be investigated to assess sensitivity of our estimates of treatment effect to alternative modeling assumptions and to evaluate additional hypotheses.

- Each dose group vs. placebo: A secondary estimand of the efficacy of mexiletine will compare 300 mg/day and 600 mg/day treatment arms vs. placebo separately, each tested at two-tailed alpha = 0.027 using Dunnett's method to control for multiple comparisons. The following SAS code specifies the linear contrasts for these comparisons:

```
estimate "3|300vsPlb|dWk 04"
    post*trtrnd*visit 0 0 -1 0  0 0 1 0  0 0 0 0 / cl divisor=1 alpha=0.027;
estimate "3|600vsPlb|dWk 04"
    post*trtrnd*visit 0 0 -1 0  0 0 0 0  0 0 1 0 / cl divisor=1 alpha=0.027;
```

- 600 mg/day vs. 300 mg/day: The relative efficacy of 300 mg/day and 600 mg/day mexiletine will be compared to infer the dosage that more effectively reduces RMT. The following SAS code specifies the linear contrast for this comparison:

```
estimate "3|600vs300|dWk 04"
    post*trtrnd*visit 0 0 0 0  0 0 -1 0  0 0 1 0 / cl divisor=1;
```

- Effect of drug washout: If we observe an effect of mexiletine on change in RMT from pre-treatment to Week 4, then we will estimate the effect of washout from Week 4 to Week 8 relative to the 4-week change over that interval among placebo participants. The following SAS code specifies the linear contrasts for these comparisons:

```
estimate "3|ActvsPlb|iWk 08"
    post*trtrnd*visit 0 0 2 -2  0 0 -1 1  0 0 -1 1 / cl divisor=2;
estimate "3|300vsPlb|iWk 08"
    post*trtrnd*visit 0 0 1 -1  0 0 -1 1  0 0 0 0 / cl divisor=1;
estimate "3|600vsPlb|iWk 08"
    post*trtrnd*visit 0 0 1 -1  0 0 0 0  0 0 -1 1 / cl divisor=1;
```

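### The SAP's criterion for the primary endpoint has the wrong sign: it counts a fall in resting motor threshold as benefit, although benefit is a rise

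*SAP*

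**What the plan says.** The primary analysis in SAP section 3.7.1 compares the two active arms, averaged, with placebo on change in RMT to Week 4, by a two-tailed Wald test at alpha 0.05. The section then says how to read the result. "A significant mean reduction in RMT from pre-treatment to the Week 4 among participants randomized to either 300 or 600 mg/day mexiletine", relative to the change on placebo, "would be considered evidence that mexiletine is effective in reducing cortical hyperexcitability". In section 3.7.2 the two doses "will be compared to infer the dosage that more effectively reduces RMT".

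The other directional statements point the opposite way:

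- SAP section 3.3.1 defines the measure as a threshold: "RMT is the magnetic field strength, measured as a percentage of the maximum stimulator output" that produces a response of at least 0.05 mV in at least 5 of 10 trials.
- Protocol section 2.1.2 reports that "RMT and SICI are reduced and MEP increased in both clinically affected familial ALS and SALS patients", and takes this as a sign of cortical hyperexcitability.
- Protocol section 4.1 sets the goal as finding whether treatment "reduces this excitability (significantly increases the RMT").
- SAP section 3.4, like protocol section 13.9, gives 80% power "if the increase in RMT relative to placebo is at least 5.3"%, and describes selecting the dose with the greater increase.

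The introduction to the SAP makes the SAP authoritative over the protocol on matters of analysis. Separately, the model description in section 3.7.1 lists "visit (4 levels: Screening, Baseline, Week 4, and Week 6"), whereas the SAP's schedule of assessments has clinic visits at Weeks 4 and 8 and none at Week 6.

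**The concern.** A two-sided test does not say which direction is good. That is left to the interpretive sentence, and the one in section 3.7.1 names the wrong direction. Read literally, a drug that lowers cortical excitability does not meet the criterion, and one that raises excitability does. The dose comparison in section 3.7.2 would likewise prefer the dose with the less favourable effect on the marker.

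If the wording stands and the trial shows a significant rise in RMT, the team must either report that its criterion was not met or reinterpret the result against its own plan after seeing the data. Either choice would weaken a positive finding on the primary endpoint.

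**Working it through.** **Direction.** RMT is a threshold, so a higher value means a stronger stimulus is needed and the cortex is less excitable. ALS lowers RMT (protocol, rationale and section 2.1.2). An effect that counters hyperexcitability therefore raises it (protocol section 4.1; SAP section 3.4). Sections 3.7.1 and 3.7.2 say the reverse in two separate sentences, so a slip in reading the PDF is implausible.

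**Inputs (SAP section 3.4).** SD of 4-week change 5.1%; target increase 5.3%; 60 randomized 1:1:1, 20 per arm; up to 10% loss, so 20 × 0.9 = 18 evaluable per arm; two-sided alpha 0.027 for each dose.

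**The plan's own power figure.**

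- SE of one dose versus placebo = 5.1 × √(2/18) = 1.70.
- Noncentrality = 5.3/1.70 = 3.12.
- Power at two-sided 0.027 = 79.7% (t, 51 df) or 81.8% (normal approximation).

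The stated 80% is reproduced, for an increase.

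**The primary contrast.** The coefficients are −2 for placebo and +1 for each active arm at Week 4, with divisor 2. The estimate is the active mean minus placebo, so a rise in RMT on mexiletine gives a positive value.

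- SE = 5.1 × √(1/18 + 1/36) = 1.47.
- For +5.3% at both doses, noncentrality = 5.3/1.472 = 3.60.

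Two-sided alpha 0.05, t with 51 df:

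| True average active effect | P(significant increase) | P(significant reduction: the written criterion) |
|---|---|---|
| +5.3% | 94.2% | about 2 × 10⁻⁸ |
| 0 | 2.5% | 2.5% |
| −5.3% | about 2 × 10⁻⁸ | 94.2% |

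**Range.** The documents give no power for the pooled contrast, and equal effects at both doses are an assumption. Two other cases:

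- Linear response at the SAP's 2.4% per 300 mg: effects of 2.4% and 4.8%, average 3.6%. P(significant increase) is about 67%; P(significant reduction) is about 6 × 10⁻⁶.
- Only one dose works, at 5.3%: average 2.65%. P(significant increase) is about 42%; P(significant reduction) is about 1 × 10⁻⁴.

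Power moves across these cases, but in each the chance of meeting the written criterion with a beneficial drug is negligible.

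**The case against.** The strongest reply is that nothing computed is wrong. The test is two-tailed, the contrast is correctly signed, and a true increase would be reported as a positive, significant estimate with a valid interval. All of that is correct, and it limits the error to interpretation and to the description of the dose comparison.

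It can also be said that the reversed sentence does not clearly govern. The precedence clause ranks the SAP above the protocol, but here the SAP also contradicts itself, because section 3.4 plans for an increase. The meaning of RMT might be called rationale, for which the SAP refers readers to the protocol. This is a fair reading and a careful analyst would probably adopt it. But the only sentence in the primary analysis section that says how to read the result still states the opposite, and the precedence clause gives no help in setting it aside.

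Three further cautions stand. RMT is a pharmacodynamic marker, so a fall is a change in the wrong direction and not demonstrated clinical harm. Protocol section 13.8 bases the choice of dose for future trials on safety and tolerability, so the reversed clause in section 3.7.2 need not determine that choice. The 94% is one favourable scenario, which is why the range is shown.

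**Conclusion.** The concern holds. The SAP's criterion for the primary endpoint is reversed, the dose comparison repeats the reversal, and both conflict with the protocol and with SAP section 3.4. Under the plan's own effect size and SD, and assuming that effect at both doses, about 94% of trials would show a significant increase and essentially none would meet the criterion as written. These figures rest on independent 4-week changes with an SD of 5.1% and 18 evaluable participants per arm. The error itself depends on none of these assumptions. Because it decides what a significant primary result means, it must be corrected. The Week 6 label is a separate clerical slip and adds nothing to the weight of this point.

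**What to change.** - SAP section 3.7.1: change the mean reduction in RMT to a mean increase in the interpretive sentence.
- SAP section 3.7.2: describe the 600 versus 300 mg/day comparison as identifying the dosage that more effectively increases RMT.
- Add one sentence to section 3.7.1 saying that contrasts are active minus placebo and that positive Week 4 estimates favour mexiletine.
- Correct Week 6 to Week 8 in the list of visit levels.

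No code, alpha, sample size or power figure changes. The cost is a wording amendment to the SAP, which should be dated before unblinding. The documents do not show the trial's current status; if unblinding has already happened, the correction should be reported openly, citing protocol section 4.1 and SAP section 3.4 as evidence of the intended direction.

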3.7.2 Secondary Analyses of the Primary Pharmacodynamic Endpoint

Several secondary analyses will be investigated to assess sensitivity of our estimates of treatment effect to alternative modeling assumptions and to evaluate additional hypotheses.

- Each dose group vs. placebo: A secondary estimand of the efficacy of mexiletine will compare 300 mg/day and 600 mg/day treatment arms vs. placebo separately, each tested at two-tailed alpha = 0.027 using Dunnett's method to control for multiple comparisons. The following SAS code specifies the linear contrasts for these comparisons:

```
estimate "3|300vsPlb|dWk 04"
    post*trtrnd*visit 0 0 -1 0  0 0 1 0  0 0 0 0 / cl divisor=1 alpha=0.027;
estimate "3|600vsPlb|dWk 04"
    post*trtrnd*visit 0 0 -1 0  0 0 0 0  0 0 1 0 / cl divisor=1 alpha=0.027;
```

- 600 mg/day vs. 300 mg/day: The relative efficacy of 300 mg/day and 600 mg/day mexiletine will be compared to infer the dosage that more effectively reduces RMT. The following SAS code specifies the linear contrast for this comparison:

```
estimate "3|600vs300|dWk 04"
    post*trtrnd*visit 0 0 0 0  0 0 -1 0  0 0 1 0 / cl divisor=1;
```

- Effect of drug washout: If we observe an effect of mexiletine on change in RMT from pre-treatment to Week 4, then we will estimate the effect of washout from Week 4 to Week 8 relative to the 4-week change over that interval among placebo participants. The following SAS code specifies the linear contrasts for these comparisons:

```
estimate "3|ActvsPlb|iWk 08"
    post*trtrnd*visit 0 0 2 -2  0 0 -1 1  0 0 -1 1 / cl divisor=2;
estimate "3|300vsPlb|iWk 08"
    post*trtrnd*visit 0 0 1 -1  0 0 -1 1  0 0 0 0 / cl divisor=1;
estimate "3|600vsPlb|iWk 08"
    post*trtrnd*visit 0 0 1 -1  0 0 0 0  0 0 -1 1 / cl divisor=1;
```

3.7.3 Secondary Endpoints

Continuous secondary pharmacodynamic and exploratory clinical and quality of life endpoints will be analyzed using the same analysis samples and models as specified for the primary pharmacodynamic endpoint in Sections 3.7.1 and 3.7.2. Variables that are strongly right-skewed (e.g., maximum MEP amplitude) will be log-transformed prior to analysis, and estimates will be back-transformed for reporting.

Weekly cramping frequency data will be analyzed in similar generalized mixed models treating the number of cramps experienced in a week as a negative binomial random variable with log link and with the log of the number of days at risk for cramps as an offset. Similarly, weekly number of days with fasciculations will be analyzed in similar generalized mixed models treating the number of days with fasciculations in a week as a binomial random variable with logit link. Because diary data are only collected after baseline, fixed effects in the model will include treatment group, post-baseline week, and baseline retrospective report of number of cramps experienced in the prior 30-day interval or the experience of fasciculations in the prior 14-day interval.

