3.2. Secondary

Secondary pharmacodynamics outcome measures will include effects on motor evoked potential (MEP) amplitude (as a % of CMAP) and cortical silent period (CSP) measured by single pulse TMS, and SICI measured by dual pulse TMS, as additional pharmacodynamic markers of cortical hyperexcitability, prior to and following treatment with mexiletine or placebo. Additionally, as a pharmacodynamic marker of peripheral motor nerve axonal hyperexcitability, threshold tracking nerve conduction studies (TTNCS) will be performed to assess strength duration time constant and recovery cycle analysis. Safety and tolerability and determination of mexiletine concentrations in blood at the time of each of the four TMS studies will also be assessed. Additionally, the effect on frequency and severity of muscle cramps and fasciculations will be assessed using a daily muscle cramps/fasciculations diary from the Baseline Visit through the Week 8 Visit and using an assessment form at the Baseline Visit. ALS Functional Rating Scale-Revised (ALSFRS-R) and slow vital capacity (SVC) will be obtained at Screening, Pre-Dose Baseline, Week 4, and Week 8 or the Final Safety Visit, if applicable as exploratory outcomes.

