Secondary outcome measures will include effects on MEP amplitude % and CSP measured by single pulse TMS, and SICI by dual pulse TMS, as additional pharmacodynamics markers of cortical hyperexcitability and TTNCs as a pharmacodynamic marker of peripheral motor axonal hyperexcitability (and therefore a potential marker for the therapeutic effect of mexiletine on muscle cramps and fasciculations), prior to and following treatment with mexiletine or placebo and then again after withdrawal of treatment. Safety and tolerability and determination of mexiletine concentrations in blood at the time of each of the two post-baseline TMS studies will also be assessed. Additionally, the effects on muscle cramps and fasciculations will be determined utilizing an Assessment Form at Baseline, and by employing a daily muscle cramping and fasciculations diary describing both frequency and severity of these symptoms from the Baseline Visit through the Week 8 Visit. Finally, ALSFRS-R, APB testing via HHD, and SVC will be obtained at Screening, Pre-Dose Baseline, Week 4, and Week 8 or the Final Safety Visit, if applicable.

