2.1 Overview

This is a multicenter, double-blind, placebo-controlled, three-arm, parallel-group, phase 2 randomized controlled trial to examine the effect of two dosages of mexiletine on neuronal excitability in ALS patients. Trial participation includes a screening visit, randomization to placebo, 300 mg/day oral mexiletine, or 600 mg/day oral mexiletine, 4 weeks of follow-up on study drug, and 4 weeks of follow-up after last dose of study drug. The trial is registered at Clinicaltrials.gov as study NCT02781454 (see <https://clinicaltrials.gov/ct2/show/NCT02781454>).

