2.2 Study Objectives

The primary objective of the trial is to determine whether treatment with mexiletine at doses of 300 mg/day or 600 mg/day suppresses cortical hyperexcitability in sporadic ALS patients relative to placebo as assessed by change in resting motor threshold (RMT) estimated from single-pulse transcranial magnetic stimulation (TMS).

Secondary objectives include evaluating the effect of mexiletine on additional pharmacodynamic markers of cortical hyperexcitability, pharmacodynamic markers of peripheral motor nerve axonal hyperexcitability by threshold tracking nerve conduction studies (TTNCS), and frequency and severity of muscle cramps and fasciculations and evaluating the safety, tolerability, and blood concentration of mexiletine.

Exploratory objectives include evaluating the effect of mexiletine on measures of clinical progression and quality of life.

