3.2.2 Clinical and Quality of Life Endpoints

Exploratory clinical and quality of life endpoints include change in the following measures made before treatment, after 4 weeks of treatment, and then again after a 4-week washout.

Clinical measures:

- ALS Functional Rating Scale-Revised (ALSFRS-R) total score,
- Slow vital capacity (SVC),
- Abductor pollicis brevis (APB) muscle strength by hand-held dynamometry (HHD),
- Muscle cramping frequency and pain, and
- Fasciculation occurrence and interference with daily life.

Quality of Life measures:

- Physical and mental summary scores from the RAND-36 Health Survey.

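### SAP 3.7.3 writes no treatment-by-week term or contrast for the cramp-count and fasciculation-day models, so as listed one effect per dose pools about four on-drug and four washout weeks.

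*SAP*

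**What the plan says.** The diary covers both phases of the trial. Protocol 3.2 describes a "daily muscle cramps/fasciculations diary from the Baseline Visit through the Week 8 Visit", and SAP 2.1 describes "4 weeks of follow-up on study drug, and 4 weeks of follow-up after last dose of study drug". Protocol 8.1.5 puts the Week 4 visit on Days 29 to 32, with the last dose the night before.

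SAP 2.2 places cramps and fasciculations among the secondary objectives: "frequency and severity of muscle cramps and fasciculations and evaluating the safety". SAP 3.2.2 lists them as exploratory endpoints and fixes the time points: "Exploratory clinical and quality of life endpoints include change in the following measures made before treatment, after 4 weeks of treatment, and then again" (the sentence ends with the 4-week washout). The Protocol Summary gives confirming the cramp effect as one reason for a further trial.

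For the primary endpoint, SAP 3.7.1 writes the treatment-by-visit term in code, "model Value = visit post*trtrnd*visit", with a Week 4 contrast. SAP 3.7.2 adds washout contrasts: "we will estimate the effect of washout from Week 4 to Week 8 relative to the 4-week change over that interval among placebo participants".

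For weekly cramp counts (negative binomial) and weekly days with fasciculations (binomial), SAP 3.7.3 calls for *similar* generalized mixed models and then gives the fixed effects: "Because diary data are only collected after baseline, fixed effects in the model will include treatment group, post-baseline week, and baseline retrospective report". No interaction and no estimate statement follows. Protocol 13.7 adds random intercepts and slopes for the cramp model, but no contrast.

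**The concern.** A model with treatment and week as main effects assumes that the treatment effect is the same in every diary week. Here half of those weeks come after dosing has stopped. The Protocol's half-life of 10 to 12 hours in normal subjects (2.2.1.1) puts five half-lives at 50 to 60 hours, so drug has largely cleared early in the washout.

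If the symptom effect fades too, the single coefficient mixes weeks with benefit and weeks without. It answers neither question in SAP 3.2.2: the effect after 4 weeks of treatment, or the change after withdrawal. SAP 3.7.5 also needs an effect of mexiletine on 4-week changes in cramps and fasciculations for its mediation analysis, and the listed model does not supply one.

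What is at stake is the trial's reading on cramps. A real on-drug effect as large as the earlier trial's could be reported as much weaker, or under some variance structures as stronger, and the washout change would go unestimated.

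**Working it through.** The plan gives no power or effect figure for cramps or fasciculations, so there is none to reproduce.

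**1. Weeks on and off drug.** The Week 4 visit falls on Days 29-32 with the last dose the night before, so dosing ends on Days 28-31. The Week 8 visit is at 56 ± 3 days, so the diary ends on Days 53-59. Off-drug diary days run from 53 - 31 = 22 to 59 - 28 = 31, with 28 on and 28 off at the nominal schedule. Scheduled week 5 (Days 29-35) can hold up to three dosing days (29, 30, 31).

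**2. Can the written contrasts be borrowed?** Those in SAP 3.7.1 and 3.7.2 are coded on four visits (Screening, Baseline and two follow-ups). The diary models have about eight post-baseline weeks and no pre-treatment rows, so that code does not apply as written.

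**3. Closed form.** A time-constant log rate ratio is a weighted mean of the weekly log rate ratios. If W is the total weight on weeks 1-4 and the effect ends with dosing, the pooled ratio is RR^W. Take RR = 0.31 (Protocol 2.1.3.2, 300 mg/day). With a random intercept only, all weeks weigh equally: W = 4/8 and 0.31^0.5 = 0.56. If benefit instead halves each week after stopping, the summed effect is 4 + 0.5 + 0.25 + 0.125 + 0.0625 = 4.9375 of 8, and 0.31^0.617 = 0.49.

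**4. Random slopes.** If these are kept, as Protocol 13.7 says for cramps, the weights become V⁻¹1 / (1'V⁻¹1), where V = ZGZ' + residual, over weekly midpoints in months. With intercept variance 1, residual 0.5 and zero covariance:
- slope variance 0: W = 0.50, ratio 0.56
- slope variance 0.1: W = 0.76, ratio 0.41
- slope variance 0.5: W = 1.05, ratio 0.29

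W can exceed 1 because late weeks can get negative weight. The last case overstates the on-drug effect.

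**5. Range.** Assumed, not in the documents: intercept SD 0.5, 1.0 or 1.5; 2, 5 or 10 cramps/week; negative binomial size 1 or 3; residual variance on the log scale 1/rate + 1/size; slope SD and correlation as shown. That makes 162 combinations. Pooled ratio for a true 0.31, no carry-over:

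| Slope SD per month | Corr. -0.3 | Corr. 0 | Corr. +0.3 |
|---|---|---|---|
| 0.05 | 0.56-0.62 | 0.55 | 0.49-0.55 |
| 0.3 | 0.48-0.65 | 0.41-0.49 | 0.25-0.46 |
| 0.6 | 0.35-0.51 | 0.30-0.39 | 0.19-0.36 |

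W runs from 0.37 to 1.41. It is below 1 (diluted) in 142 combinations and above 1 (exaggerated) in 20. A second normal-approximation grid over the same ranges gave W from 0.33 to 1.35, that is 0.31^0.33 = 0.68 to 0.31^1.35 = 0.21. Together the range is about 0.2 to 0.7.

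**6. Check with a full mixed model.** The listed negative binomial model was fitted to large simulated data (5 cramps/week, size 1 or 3, intercept SD 0.5 or 1.0, correlation 0). Without carry-over it gave 0.54-0.58, 0.44-0.50 and 0.34-0.40 at slope SD 0.05, 0.3 and 0.6. With benefit halving weekly it gave 0.47-0.49, 0.40-0.45 and 0.32-0.37. Adding treatment by period to the no-carry-over data returned 0.30-0.32 on drug and 0.94-1.03 in washout (true values 0.31 and 1).

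**The case against.** The best defence is that the interaction was meant. The paragraph calls these models *similar* to the primary one, whose central term is treatment by post-baseline visit. The sentence about fixed effects mainly explains why a baseline covariate replaces the shared baseline, and *will include* need not be exhaustive. It is also uneven to read random slopes into *similar* and not the interaction. SAP 3.7.5 confirms that a 4-week effect on these symptoms is wanted.

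This stands in part. A reader might infer that the SAP rules out a time-varying effect; the wording does not go that far. But no passage writes the term for these models. Even with it, nothing says which weekly effect, or which average, is the reported result.

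A reader might also infer that the cramp effect will be halved, or at least always biased towards no effect. The documents do not support that. The 0.56 needs equal week weights and a complete loss of benefit, and other assumed covariances give exaggeration. The 142 of 162 is a count over chosen scenarios, not a probability. Nor does the plasma half-life show how fast a cramp effect fades.

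On scope, the sentence covers cramp counts and days with fasciculations. Cramp pain, if treated as continuous, arguably falls under the first paragraph of SAP 3.7.3 and its Week 4 and washout contrasts. These endpoints are exploratory in SAP 3.2.2 and carry no power claim, which limits the consequence.

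**Conclusion.** The point holds as a gap in specification. Followed as listed, SAP 3.7.3 gives one time-constant effect per dose, which does not estimate the endpoints in SAP 3.2.2 or the 4-week effect used in SAP 3.7.5. How far it reflects the on-drug weeks is set by the estimated random-effect covariance, so the quantity reported is not fixed in advance.

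The illustrative sizes rest on a ratio of 0.31 taken from one dose of the earlier trial (600 mg/day was not studied there), on benefit ending with dosing, and on assumed cramp rate, dispersion and variances. If the effect persists fully through Week 8 there is no distortion. No loss of power can be quantified for this trial from the documents. The change should be made because it is cheap and bears on a stated aim of the trial.

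**What to change.** In SAP 3.7.3, write treatment by post-baseline week, or treatment by period (weeks 1-4 against weeks 5-8), into both diary models. Before unblinding:
- name one on-drug contrast versus placebo, pooled and for each dose, as the reported effect;
- add a separate washout contrast, as SAP 3.7.2 does for RMT;
- state to which period the week containing Days 29-31 belongs.

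The cost is SAP wording, one model term and the named contrasts, with no new data. The downside is a small loss of power if the effect persists after stopping. In a normal-approximation grid over the ranges in the working (18 placebo against 36 active, ratio 0.31, two-sided 0.05), the weeks 1-4 contrast cost at most 5 percentage points in that case.
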